2.2 Table of In-Text Figures

Figure 1	Study Sequence	27
----------	----------------------	----

3 Synopsis

Sponsor:

Melinta Therapeutics, LLC

Drug Substance:

Baxdela® (delaflloxacin)

IRAS ID:

1009679

Title of Study:

A Phase 1, Single Part, Partially Randomised, Open-Label Study to Evaluate the Relative Bioavailability of a Taste-Masked Delafloxacin Powder for Oral Suspension with Oral Delafloxacin Tablet Reference in Healthy Subjects

Principal Investigator:
**Study Centre:**

Quotient Sciences, [name]

Objectives and Endpoints:

Objectives	Endpoints
Primary To determine the relative bioavailability of delafloxacin Powder for Oral Suspension compared to that of oral delafloxacin Tablet reference	Results of the formal statistical analysis of overall exposure (AUC) for delafloxacin Powder for Oral Suspension, compared to oral delafloxacin Tablet reference
Secondary To determine the PK of delafloxacin Powder for Oral Suspension formulation	PK parameters for delafloxacin: Tlag, Tmax, Cmax, AUC(0-24), AUC(0-last), AUC(0-inf), lambda-z, Frel, T1/2, CL/F, Vz/F, and MRT, as applicable
To determine the relative bioavailability of delafloxacin Powder for Oral Suspension in the fed and fasted state	Results of the formal statistical analysis of overall exposure (AUC) for delafloxacin Powder for Oral Suspension in the fed state compared to the fasted state
To provide additional safety and tolerability information for orally administered delafloxacin	Assessment of adverse events (AEs), vital signs, electrocardiograms (ECGs), physical examinations, and clinical laboratory tests
Exploratory To evaluate the taste/palatability attributes (smell, sweetness, bitterness, flavour, mouthfeel/texture, grittiness, and aftertaste) and overall acceptability of delafloxacin Powder for Oral Suspension	Results of the taste questionnaire

Methodology:

This is a Phase 1, single centre, single part, partially randomised, open-label, relative bioavailability study in healthy subjects.

It is planned to enrol approximately 16 healthy male and healthy non-pregnant, non-lactating female subjects.

It is planned to administer up to four regimens:

Period	Regimen	Investigational Medicinal Product	Dose	Route of Administration
1 and 2	A	delafloxacin Tablet (reference)	450 mg	Oral, Fasted
	B	delafloxacin Powder for Oral Suspension, reconstituted with orange flavoured vehicle	450 mg	Oral, Fasted
3	C	delafloxacin Powder for Oral Suspension, reconstituted with orange flavoured vehicle	450 mg or XX mg	Oral, Fed or Oral, Fasted
4 (optional)	D	delafloxacin Powder for Oral Suspension, reconstituted with orange flavoured vehicle	XX mg or YY mg	Oral, Fed or Oral, Fasted

The order in which regimens are dosed may be subject to change due to logistical reasons

The effect of food on the PK of a novel delafloxacin Powder for Oral Suspension formulation may be explored in Period 3 or optional Period 4, by administering investigational medicinal product (IMP) after a high-fat breakfast. The effect of increasing or decreasing the dose level may also be explored.

There will be an interim decision meeting after Periods 2 and 3 to review the PK and safety data for up to 48 hours post-dose from preceding periods, in order to determine the dose and prandial state for Regimen C and Regimen D (if applicable).

There will be a minimum washout of 4 days between dosing in Periods 1 and 2. The intervals between Periods 2 and 3, and Period 3 and optional Period 4, will require a minimum of 14 days, to permit the interim decision process and IMP manufactures.

Study Design:

Subjects will undergo preliminary screening procedures for the study at the screening visit (Day -28 to Day -2).

Periods 1 and 2

Subjects will be admitted in the morning on the day before dosing (Day -1) in Period 1. Subjects will receive a snack in the evening, after which they will fast overnight from all food and drink (except water) for a minimum of 10 hours. Subjects will be administered IMP on the morning of Day 1 in the fasted state. Subjects will complete a written taste/palatability questionnaire individually and privately following IMP administration (Regimen B only).

Subjects will be randomised in a 1:1 ratio to one of two sequences (AB or BA) immediately prior to dosing in Period 1, for allocation of regimens across Periods 1 and 2. Blood and urine samples will be collected at regular intervals for PK and safety analysis, as applicable, from admission until 48 hours post-dose during each period. Subjects will remain resident in the clinical unit during the washout period (minimum 4 days) between Periods 1 and 2. Subjects will be discharged from the clinical unit at 48 hours post-dose (Day 3) in Period 2.

Following dosing of Regimens A and B, there will be an interim decision meeting to review available PK and safety data to decide the dose level and prandial state for Regimen C. The Investigator and Sponsor will decide whether to continue to evaluate a 450 mg dose level of delafloxacin Powder for Oral Suspension following a high-fat breakfast, or to evaluate an alternative dose level in the fasted state.

Period 3

Subjects will be admitted in the evening on the day before dosing (Day -1). Subjects will fast overnight from all food and drink (except water) for a minimum of 10 hours, and will

be administered IMP on the morning of Day 1 in the fasted state (if a different dose level is selected), or approximately 30 minutes after a high-fat breakfast (if a change to prandial state is selected). Subjects will complete a written taste/palatability questionnaire individually and privately following IMP administration.

Blood and urine samples will be collected at regular intervals for PK and safety analysis, as applicable, from admission until 48 hours post-dose (Day 3), at which time subjects will be discharged from the clinical unit.

Following dosing of Regimen C, there will be an interim decision meeting to review available PK and safety data, to decide whether to proceed with optional Period 4 or whether to end the study. If it is decided to end the study, a follow-up phone call will take place on Day 6 ± 1 to ensure the ongoing wellbeing of subjects. If a subject reports any AEs that present a cause for concern, they will be required to attend the clinical unit for an (unscheduled) follow-up visit. End of study is defined as completion of the last follow-up phone call or unscheduled follow-up visit. If it is decided to proceed with optional Period 4, the dose level and prandial state for Regimen D will be determined; the Investigator and Sponsor will decide whether to continue to evaluate the dose level selected for Regimen C following a high-fat breakfast, or to evaluate an alternative dose level in the fasted state.

Optional Period 4

Subjects will be admitted in the evening on the day before dosing (Day -1). Subjects will fast overnight from all food and drink (except water) for a minimum of 10 hours, and may be administered IMP on the morning of Day 1 in the fasted state (if a different dose level is selected), or approximately 30 minutes after a high-fat breakfast (if a change to prandial state is selected). Subjects will complete a written taste/palatability questionnaire individually and privately following IMP administration.

Blood and urine samples will be collected at regular intervals for PK and safety analysis, as applicable, from admission until 48 hours post-dose (Day 3), at which time subjects will be discharged from the clinical unit. A follow-up phone call will take place on Day 6 ± 1 to ensure the ongoing wellbeing of subjects. If a subject reports any AEs that present a cause for concern, they will be required to attend the clinical unit for an (unscheduled) follow-up visit; completion of the last follow-up phone call or unscheduled follow-up visit will be considered the end of the study.

Number of Subjects Planned:

The study is exploratory, and no formal sample size calculation has been made. Based on experience from previous studies of a similar design, a sample size of 16 subjects and a minimum of 12 evaluable subjects is considered sufficient to meet the objectives of the study.

An evaluable subject for the relative bioavailability assessment will have received delafloxacin Powder for Oral Suspension (test) and the oral delafloxacin Tablet (reference) at the same dose level, in the fasted state, and have evaluable PK and safety data to 48 hours post-dose.

An evaluable subject for the food effect assessment will have received delafloxacin Powder for Oral Suspension in the fed and fasted state, at the same dose level, and have evaluable PK and safety data to 48 hours post-dose.

Subjects withdrawn due to an IMP-related AE will not be replaced.

Subjects who are withdrawn for other reasons may be replaced as required, by agreement between the Investigator and the Sponsor, to ensure sufficient evaluable subjects. Up to 4 replacement subjects may be enrolled into the study. The maximum number of subjects that may be dosed is 20.

Duration of Study:

Subjects will receive single administrations of delafloxacin on up to 4 separate occasions. The estimated time from screening until the follow-up phone call is approximately 14 weeks.

Investigational Medicinal Product, Dose and Mode of Administration:

The following IMPs will be used in this clinical study:

IMP Name	Dose	Route of Administration
delafloxacin Tablet, 450 mg (reference)	450 mg ^a	Oral, Fasted
delafloxacin Powder for Oral Suspension, 300 – 600 mg ^b	300 mg – 600 mg ^c	Oral, Fasted or Fed

^a Each oral delafloxacin Tablet contains 649.35 mg delafloxacin meglumine (salt form) equivalent of 450 mg free acid

^b Delafloxacin Powder for Oral Suspension will be reconstituted with orange flavoured vehicle

^c Delafloxacin Powder for Oral Suspension contains 439.5 mg to 878.9 mg delafloxacin meglumine (salt form) equivalent to 300 mg to 600 mg free form

Oral tablets will be administered with a total of 240 mL of water. If required, additional water may be given with the IMP in 50 mL aliquots.

Immediately after administration of delafloxacin Powder for Oral Suspension, the dosing vessel will be rinsed with water and subjects will consume the rinse solution. Subjects will then consume further water to a total volume of 240 mL (including the dosing volume and volume used to rinse the dosing vessel). If required, additional water may be given with the IMP in 50 mL aliquots.

Study Assessments:

The following blood and urine samples will be collected, and assessments performed, at specified time points:

- Delafloxacin in plasma for PK analysis.
- Taste/palatability questionnaire (following delafloxacin Powder for Oral Suspension [i.e., test] regimens only).
- Safety assessments comprising AE monitoring, clinical laboratory tests (clinical chemistry, haematology and urinalysis), physical examinations, single 12-lead ECGs and vital signs.

Statistical Analysis:

PK parameters will be calculated using standard non-compartmental analysis to obtain at a minimum: Tlag, Tmax, Cmax, AUC(0-24), AUC(0-last), AUC(0-inf), Lambda-z, Frel, T1/2, CL/F, Vz/F, and MRT for delafloxacin in plasma, as applicable.

Descriptive summaries for all PK, safety, and taste data by regimen, as applicable, will be provided (including changes from baseline as required).

Formal statistical analysis will be performed on the PK parameters Cmax, AUC(0-last), and AUC(0-inf) to assess relative bioavailability. The PK parameters will undergo a natural logarithmic transformation and will be analysed using a mixed effect model, with terms for sequence and regimen as fixed effects, and subject within sequence as a random effect.

Formal statistical analysis will also be performed on the PK parameters Cmax, AUC(0-last), and AUC(0-inf) to assess for the effects of food on delafloxacin Powder for Oral Suspension regimens administered at the same dose level. The PK parameters will undergo a natural logarithmic transformation and will be analysed using a mixed effect model, with terms for regimen as fixed effect, and subject as a random effect.

Additionally, formal statistical analysis may be performed on the log-transformed, dose-corrected PK parameters Cmax, AUC(0-last), and AUC(0-inf) to assess dose

proportionality, if two dose levels of delafloxacin Powder for Oral Suspension are administered in the same prandial state, using a mixed effect model, with terms for regimen as a fixed effect and subject as a random effect.

4 List of Abbreviations

Abbreviation	Definition
ABSSSI	acute bacterial skin and skin structure infections
ADR	adverse drug reaction
AE	adverse event
ALT	alanine aminotransferase
BID	twice daily
BMI	body mass index
CABP	community acquired bacterial pneumonia
CHMP	Committee for Medicinal Products for Human Use
CI	confidence interval
CNS	central nervous system
COVID-19	Coronavirus Disease 2019
CSPM	Clinical Sample Processing Manual
CV%	coefficient of variation
CYP	cytochrome P450
DMP	data management plan
EC	ethics committee
ECG	electrocardiogram
eCRF	electronic case report form
EMA	European Medicines Agency
FDA	US Food and Drug Administration
FSH	follicle stimulating hormone
GCP	Good Clinical Practice
GI	gastrointestinal
GMR	geometric mean ratios
HBsAg	hepatitis B surface antigen
HCV Ab	hepatitis C virus antibody
HIV	human immunodeficiency virus
HRT	hormone replacement therapy
IB	Investigator's Brochure
ICF	informed consent form
ICH	International Council for Harmonisation of Technical Requirements for Pharmaceuticals for Human Use
IMP	investigational medicinal product
ISF	Investigator Site File

IV	intravenous
MRSA	methicillin resistant Staphylococcus aureus
MHRA	Medicines and Healthcare products Regulatory Agency
PIS	Participant Information Sheet
PK	pharmacokinetic(s)
QA	quality assurance
QC	quality control
QTc	corrected QT interval
QTcF	corrected QT interval by Fridericia's formula
RAP	Reporting and Analysis Plan
SAC	safety advisory committee
SAE	serious adverse event
SAR	serious adverse reaction
SARS-CoV-2	severe acute respiratory syndrome coronavirus 2
SOP	standard operating procedure
SUSAR	suspected unexpected serious adverse reaction
TEAE	treatment-emergent adverse event

The pharmacokinetic definitions used in this study are presented in [Section 15.3](#).

5 Background Information

5.1 Introduction

Delaflloxacin (also noted as RX-3341, ABT-492, ABT-319492, or WQ-3034, and currently marketed in multiple countries, including in the US as Baxdela® [1], and in the EU as Quofenix® [2]) is an approved, broad-spectrum anionic fluoroquinolone antibiotic for the treatment of adults with acute bacterial skin and skin structure infections (ABSSI) and community-acquired bacterial pneumonia (CABP). Melinta Therapeutics, LLC (Melinta; formerly Rib-X Pharmaceuticals) licensed Baxdela® from Wakunaga Pharmaceutical Company in Japan. Prior to its licensing by Melinta, the compound was developed by Abbott Laboratories as an oral formulation (ABT-492) for use in the treatment of community-acquired infections.

Throughout the world, the incidence of antimicrobial resistance has increased for bacterial infections in hospital and community settings. *Staphylococcus aureus*, especially methicillin resistant *S. aureus* (MRSA), ranks as the most frequently isolated pathogen in hospital intensive care units in the US. The Centers for Disease Control and Prevention estimates that MRSA is responsible for more than 300,000 infections, resulting in more than 10000 deaths per year in the US [3]. The risk factors for MRSA are constantly evolving, and the distinction between community-acquired MRSA and hospital-acquired MRSA is becoming less clear from a therapeutic standpoint because of overlapping susceptibility patterns.

Whilst gram-positive pathogens, including *streptococci* and *staphylococci*, are the most common bacteria associated with ABSSI, gram-negative pathogens must also be considered as causative when selecting initial empiric therapy, particularly in patients with certain comorbid conditions such as diabetes, surgical site infections, anal and perianal region infections, and compromised vascular perfusion [4]. Drug-resistant bacteria are demonstrating alarming trends as causative pathogens in skin and soft tissue infections. Delafloxacin exhibits a concentration-dependent bactericidal activity against gram-positive and gram-negative bacteria in vitro [1].

Baxdela® is indicated in adults for the treatment of ABSSIs and CABP, and can be administered as an intravenous (IV) infusion or as an oral tablet [1]. Melinta is developing an oral suspension formulation as a potential therapeutic for CABP in paediatric patients (target age group 2 months to 18 years). Safety and effectiveness in paediatric patients below the age of 18 years have not been established [5].

This study will evaluate the relative bioavailability of a novel powder for oral suspension formulation of Baxdela®, intended for weight-based paediatric dosing, relative to that of the licensed Baxdela® oral tablet, in approximately 16 healthy adults. Food effect and effect of a change in dose level on bioavailability of the novel powder for oral suspension will also be evaluated.

5.2 Investigational Medicinal Products

The investigational medicinal products (IMPs) that will be used in this clinical study are presented in [Table 1](#).

Table 1 Investigational Medicinal Products

IMP Name	Dose	Route of Administration
delafloxacin Tablet, 450 mg (reference)	450 mg ^a	Oral, Fasted
delafloxacin Powder for Oral Suspension, 300 – 600 mg ^b	300 mg – 600 mg ^c	Oral, Fasted or Fed

^a Each oral delafloxacin Tablet contains 649.35 mg delafloxacin meglumine (salt form) equivalent of 450 mg free acid

^b Delafloxacin Powder for Oral Suspension will be reconstituted with orange flavoured vehicle

^c Delafloxacin Powder for Oral Suspension contains 439.5 mg to 878.9 mg delafloxacin meglumine (salt form) equivalent to 300 mg to 600 mg free form

Delafloxacin Powder for Oral Suspension is an un-licensed medicinal product for use only in the proposed clinical trial.

The oral delafloxacin Tablets to be used in this study are marketed in the US (as Baxdela[®]). They are to be used in the clinical trial within the terms of the marketing authorisation, other than being administered to healthy volunteers.

Only subjects enrolled in the study may receive study treatment and only authorised site staff may supply or administer study treatment. All study treatments will be stored in a secure, environmentally-controlled, and monitored (manual or automated) area in accordance with the labelled storage conditions with access limited to the Investigator and authorised site staff.

Where Quotient Sciences is manufacturing the IMPs, suitability of the manufacturing process will be documented in a Pharmaceutical Development and Control Strategy Report.

IMPs will be reconciled and destroyed in accordance with the study-specific quality agreement and technical addendum.

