5.3.2 Clinical Findings

Delafloxacin is a broad-spectrum anionic fluoroquinolone antibiotic, approved for administration in adults as IV infusion and oral tablet formulations, and has been marketed for the treatment of adults with ABSSSI and CABP as Baxdela® [1] since 2017 and 2019, respectively, in the US, and as Quofenix® [2] since 2019 and 2021, respectively, in the EU. A total of 32 clinical studies have been completed with oral and IV delafloxacin, including twenty-four Phase 1, four Phase 2 and four Phase 3 studies. In total, approximately 3117 subjects and patients have received delafloxacin in completed trials.

Following oral tablet administration, peak plasma concentrations of delafloxacin occur at a median of 0.8 hours (range 0.5 hours to 4 hours). Delafloxacin maximum mean plasma concentration measured after dosing (Cmax) and area under the mean concentration time curve (AUC) increase proportionally to dose over the range of 50 mg to 1600 mg and 200 mg to 1600 mg, respectively. The absolute bioavailability of oral delafloxacin Tablet is 58.8%. The administration of delafloxacin with food delays absorption and reduces Cmax, but does not alter total absorption (AUC). Thus, delafloxacin can be given without regard to food. The 450 mg delafloxacin commercial tablet and 300 mg IV Captisol® lyophilised formulations are bioequivalent with regard to total exposure (AUC). Multiple oral BID dosing of delafloxacin 450 mg tablets to steady-state results in 1.35-fold higher concentrations of delafloxacin. Delafloxacin is well distributed after IV and oral tablet administration, with a mean volume of distribution at steady state of 34.2 L, which is just below total body water (42 L). Plasma protein binding is approximately 84%.

Delafloxacin is primarily metabolised by glucuronidation, with oxidative metabolism representing <1% of the dose. The glucuronidation of delafloxacin is primarily mediated by UGT1A1 and UGT1A3. Unchanged parent drug is the predominant component in plasma; no single metabolite represents ≥ 20% of circulating components. Delafloxacin is eliminated primarily by renal excretion, but biliary clearance and transintestinal elimination may also play a role. Metabolism accounts for about 20% of the elimination of delafloxacin.

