15.1 Sample Size Justification

The study is exploratory, and no formal sample size calculation has been made. Based on experience from previous studies of a similar design, a sample size of 16 subjects and a minimum of 12 evaluable subjects is considered sufficient to meet the objectives of the study.

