9.1.1 Definition of Plasma PK Parameters

Plasma PK parameter definitions are provided in [Table 2](#).

Table 2 Plasma PK Parameter Definitions and Rounding Specifications

Parameter	Definition	Unit	DP or SF	No. of DP/SF
Tlag	Time prior to the first measurable concentration	h	DP	2
Tmax	Time of maximum observed concentration	h	DP	2
Cmax	Maximum observed concentration	mass unit/mL	SF	3

Parameter	Definition	Unit	DP or SF	No. of DP/SF
AUC(0-24)	Area under the curve from time 0 to 24 h post dose	mass unit.h/mL	SF	3
AUC(0-last)	Area under the curve from time 0 to the time of last measurable concentration	mass unit.h/mL	SF	3
AUC(0-inf)	Area under the curve from time 0 extrapolated to infinity	mass unit.h/mL	SF	3
AUCextrap	Area under the curve from time of the last measurable concentration to infinity as a percentage of the area under the curve extrapolated to infinity	%	DP	2
T1/2	Terminal elimination half-life	h	DP	2
Lambda-z	First order rate constant associated with the terminal (log-linear) portion of the curve	1/h	DP	4
CL/F	Total body clearance calculated after a single extravascular administration where F (fraction of dose bioavailable) is unknown.	mL/min	SF	3
Vz/F	Apparent volume of distribution based on the terminal phase calculated using AUC(0-inf) after a single extravascular administration where F (fraction of dose bioavailable) is unknown	L	SF	3
MRT(0-last)	Mean residence time from time 0 to time of the last measurable concentration	h	DP	2
MRT(0-inf)	Mean residence time extrapolated to infinity	h	DP	2
Frel Cmax	Relative bioavailability based on Cmax	%	DP	2
Frel AUC(0-last)	Relative bioavailability based on AUC(0-last)	%	DP	2
Frel AUC(0-inf)	Relative bioavailability based on AUC(0-inf)	%	DP	2
lambda-z lower*	Lower limit on time for values to be included in the calculation of lambda-z	h	DP	2
lambda-z upper*	Upper limit on time for values to be included in the calculation of lambda-z	h	DP	2

DP = decimal places; NA = not applicable; SF = significant figures

* = these values should be listed but omitted from the descriptive statistics

If 2 dose levels are administered of the same formulation in the same prandial state, then dose-normalised PK parameters will be calculated for the assessment of dose proportionality.

Dose will be used in the calculation of relevant PK parameters as per [Table 3](#).

Table 3 Dose Specifications

Dose (nominal/actual)	Nominal
Precision	As per protocol

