Non-dose corrected relative bioavailability (Frel) will be calculated as follows:

$$Frel = \left\{ \frac{AUC \text{ or } Cmax \text{ (test)}}{AUC \text{ or } Cmax \text{ (reference)}} \right\} \times 100$$

Frel will be calculated using Cmax, AUC(0-last) and AUC(0-inf). If for any reason the AUC(0-inf) is not calculable then an alternative or additional AUC over a partial area may be used to calculate Frel for all subjects.

The following comparisons will be made:

- 450 mg delafloxacin Powder for Oral Suspension (test) vs delafloxacin Tablet (reference) (Regimen A)
- 450 mg delafloxacin Powder for Oral Suspension fed (test) vs delafloxacin Powder for Oral Suspension fasted (reference)

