9.5.1 Relative Bioavailability

Statistical analyses will be performed on the PK parameters Cmax, AUC(0-last), and AUC(0-inf). The parameters will undergo a natural logarithmic transformation and will be analysed using a mixed effects model. The model will include terms for regimen, period and sequence as fixed effects, and subject within sequence as a random effect.

The following comparison is of interest (test vs reference):

- Regimen B (delafloxacin Powder for Oral Suspension) vs Regimen A (delafloxacin Tablet [reference])

Subjects will be included in the analysis if they have data for both test and reference in regimens included in the comparison above.

The adjusted means, including differences from the pairwise comparisons and their associated 90% CIs obtained from the model, will be back transformed on the log scale to obtain adjusted geometric mean ratios (GMRs) and 90% CIs of the ratios.

The statistical analysis will be performed using actual regimen received and planned sequence, as detailed on the randomisation schedule. The model will be fitted using the SAS Software procedure PROC MIXED. The method will be specified as Restricted Maximum Likelihood and the denominator degrees of freedom for the fixed effects will be calculated using Kenward and Roger's method [4]. The following is an example of the SAS Software code that will be used:

```
PROC MIXED DATA= METHOD=REML ORDER=INTERNAL;
  CLASS TRTAN APERIODN TRTSEQPN;
  MODEL LVAR = TRTAN APERIODN TRTSEQPN / OUTP=PRED DDFM=KR;
  RANDOM SUBJIDN(TRTSEQPN);
  ESTIMATE <relevant pairwise treatment comparisons> / CL ALPHA=0.10;
  LSMEANS TRTAN / ALPHA=0.10;
  ODS OUTPUT LSMEANS=MEANS ESTIMATES=EST;
RUN;
```

where

- LVAR is the natural log transformed PK parameter of interest
- SUBJIDN is the numeric subject identifier variable
- TRTAN is the numeric treatment variable for the actual treatment received
- TRTSEQPN is the numeric sequence variable for the planned sequence received
- APERIODN is the numeric period variable

If there are any deviations from the planned treatment, then the analysis model specified or methods of analysis may be re-evaluated, as appropriate. Details of any deviations from the planned analysis will be documented in the CSR.

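### Do the salt masses in the protocol's product table mean that the powder and tablet doses of 450 mg are unequal?

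*Protocol*

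**What the plan says.** Table 1 in Protocol section 5.2 gives the active content of the two products in its footnotes. For the tablet: "Each oral delafloxacin Tablet contains 649.35 mg delafloxacin meglumine (salt form) equivalent of 450 mg free acid". For the powder: "Delafloxacin Powder for Oral Suspension contains 439.5 mg to 878.9 mg delafloxacin meglumine (salt form) equivalent to 300 mg to 600 mg free form". The synopsis repeats both statements with the same figures. Table 2 in Protocol section 8.1 sets 450 mg for Regimen A (tablet) and for Regimen B (powder), the two arms of the primary comparison.

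Section 5.2 also says that the tablet is the product marketed in the US and that the powder is un-licensed and for this trial only. Where the clinical site makes a product, section 5.2 refers the suitability of the manufacturing process to a separate development and control report.

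On the analysis side, SAP section 9.1.1 introduces the individual ratios with "Non-dose corrected relative bioavailability (Frel) will be calculated as follows" and defines Frel as test over reference. SAP section 9.5.1 describes the primary model: "The model will include terms for regimen, period and sequence as fixed effects, and subject within sequence as a random effect". Where a dose is needed to derive a PK parameter, Table 3 of SAP section 9.1.1 sets it to nominal.

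**The concern.** Both footnotes name delafloxacin meglumine, and both equate a mass of it with a mass of the free drug. One salt on one basis should have one conversion factor, and here there are two. The wording differs as well (free acid for the tablet, free form for the powder), without a statement that the two mean the same thing.

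The primary objective compares the two products at the same dose level. If the powder really held about 1.5% more free drug at nominal 450 mg, that excess would appear as extra bioavailability. Frel is not dose corrected, and the model has no term for dose or content, so nothing in the planned analysis would remove it. Such a shift is systematic, so more subjects would not reduce it.

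**Working it through.** **Inputs** (Protocol section 5.2, Table 1 footnotes a and c; the synopsis agrees): tablet 649.35 mg salt for 450 mg free; powder 439.5 mg for 300 mg and 878.9 mg for 600 mg.

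**Step 1. Factor = salt mass / free mass, with the rounding range of the printed salt mass.**

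- Tablet: 649.35 / 450 = 1.4430; range 649.345/450 to 649.355/450 = 1.44299 to 1.44301.
- Powder, low end: 439.5 / 300 = 1.4650; range 439.45/300 to 439.55/300 = 1.46483 to 1.46517.
- Powder, high end: 878.9 / 600 = 1.46483; range 878.85/600 to 878.95/600 = 1.46475 to 1.46492.

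The two powder figures share one factor, 1.46483 to 1.46492. They agree with each other and differ from the tablet.

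**Step 2. Gap.** 1.46483 / 1.44301 − 1 = 1.51%, up to 1.46492 / 1.44299 − 1 = 1.52%.

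**Step 3. Can rounding of the free masses close it?** With each free mass allowed ±0.5 mg:

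- tablet 649.35/450.5 to 649.35/449.5 = 1.4414 to 1.4446;
- powder, low end, 439.5/300.5 to 439.5/299.5 = 1.4626 to 1.4674;
- powder, high end, 878.9/600.5 to 878.9/599.5 = 1.4636 to 1.4661.

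There is still no overlap, so the mismatch is real.

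**Step 4. What it would mean at 450 mg.** The powder mass at 450 mg is not printed. On the common powder factor it is 450 × 1.46483 to 450 × 1.46492, about 659.2 mg, or 9.8 to 9.9 mg more salt than the tablet. Two readings fit these figures:

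- *Different content bases.* If the powder's drug substance has about 0.985 of the free content per mg of the tablet's (1.4430 / 1.4649 = 0.985), then 659.2 × 0.985 ≈ 649.3 mg on the tablet's basis. Both products then deliver 450 mg free, and both footnotes are true.
- *Same material, printed masses dispensed.* The powder then holds 659.2 / 1.4430 ≈ 456.8 mg free, and 456.8 / 450 = 1.015. With exposure proportional to dose, GMR and Frel would rise by about 1.5%.

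**Step 5. Would the second reading call for a different analysis?** No. A constant content ratio moves every log ratio by the same amount, ln(1.015) ≈ 0.015. The GMR and both 90% limits could be divided by 1.015 after the fact, with no change to the model or to the interval width on the log scale. The food-effect and dose-proportionality comparisons set powder against powder, and both printed powder masses share one factor, so the mismatch cancels there.

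**The case for a change.** The best case for acting is that this is no isolated misprint. The same figures stand in the synopsis and in Table 1, and the two powder masses agree with each other, which points to a different conversion for the powder and not to a slip in one number. Neither document mentions a correction for potency, water content or overage. If there is one, footnote c presents a corrected mass as a plain salt equivalence. The powder is meant for weight-based paediatric dosing, so the basis of its content should be traceable, and one sentence would settle it.

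Much of this stands: the factors differ, the documents do not say why, and a reader cannot work out the reason. What does not stand is the step to an error or a bias. Each footnote is consistent within itself and describes a different product. Both declare equivalence to the nominal free dose, so as printed the free doses are equal. A larger salt mass is what equal free content would require if the powder's drug substance had lower content. Nothing says that both products use the same material or that the printed masses are the weighed masses. Proportionality is reported only for oral delafloxacin in general: Protocol section 5.3.2 says that Cmax and AUC "increase proportionally to dose over the range of 50 mg to 1600 mg and 200 mg to 1600 mg, respectively", which is not evidence on this powder. Leaving dose correction out of Frel is also ordinary when both arms have the same nominal dose.

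**Conclusion.** The 1.51 to 1.52% mismatch between the two conversion factors is certain. An effect on the trial is not shown. The demonstrated shift in the primary GMR and Frel is nil. The conditional shift is about +1.5%, and it rests on three assumptions together: the same salt material in both products, printed masses equal to dispensed masses, and dose-proportional exposure for the powder. The first two have no support in the documents.

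What is missing is a stated basis for each mass. Those figures belong to product records outside the protocol and SAP. The footnotes and their synopsis copies have to be reconciled against those records, and the documents do not show which figure, if either, is wrong. That is an editorial clarification. If it did reveal a real content difference, an analyst would mention about 1.5% when interpreting the powder/tablet ratio, and the planned model would already give everything needed to do so. Protocol section 15.1 states: "The study is exploratory, and no formal sample size calculation has been made". Section 15.4 adds that no formal hypothesis is tested, so no pass/fail decision depends on a shift of this size. No change to the design or the analysis follows.
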